Effect of renin-angiotensin-system blockade on urinary free light chains in patients with type 2 diabetes mellitus

Abstract : - Specific aims page

Type 2 diabetes mellitus (DM) is an epidemic. Nearly 24 million people older than 20 years of age have DM(1). DM is the leading cause of chronic kidney disease (CKD)(2). Currently, more than 20 million adults > 20 years of age have CKD (3). More than 35% of people aged > 20 years of age with DM have CKD.

Measuring albuminuria remains the key tool for screening diabetic patients for nephropathy. Albumin adjusted for urinary creatinine as assessed by the spot urine microalbumin creatinine ratio (UMACR) is used to diagnose (>30 ml/min) kidney disease, assess adequacy of treatment and monitor progression of CKD. But, UMACR does not distinguish those that will have progression of CKD from those that will not. Stage of chronic kidney disease is assessed by the estimated glomerular filtration rate (eGFR). However, tight glycemic control has shown not to decrease the incidence or progression of CKD (4) and the Third NHANES data (5) reveals that not all the patients with DM with CKD have albuminuria. Limitations of UMACR have led to an international working group to call for research into new biomarkers of diabetic nephropathy(6) that either improve the likelihood of prediction of progression to CKD as a clinical marker of diabetic kidney disease. Free light chains (FLCs) are low-molecular-mass molecules (kappa and lambda light chains), which are by-products of normal immunoglobulin synthesis(7) and are normally excreted through the kidneys. Presence of light chains in the urine is a marker of tubular dysfunction. In patients with impaired kidney function, serum concentrations and urinary excretion of polyclonal FLCs have been noted to be increased. Increased excretion of FLCs and other low-molecular weight proteins [cystatin C, NGAL] in the urine may contribute to progression of chronic kidney disease. Higher Cystatin C has demonstrated to be related to development of albuminuria(8). Neutrophil gelatinase-associated lipocalin (NGAL) excretion in the urine is a marker of tubular injury in the kidney and has been shown to be elevated in subjects with type 1 and 2 DM.(9) Our data is consistent with the published data demonstrating that urinary FLC (UFLC) are elevated in patients with diabetes and hypertension as compared to healthy controls. Angiotensin-converting enzyme inhibitors (Ace Inh) and angiotensin II receptor blockers (ARB) class of drugs are renoprotective in nature and are the first line therapy for treatment of diabetic nephropathy(10). There is no longitudinal data evaluating the effect of Ace Inh and ARB class of drugs on UFLCs.

Our **hypothesis** is that UFLCs are increased in patients with DM with and without nephropathy, and that treatment with Ace Inh and/or ARB will decrease UFLCs in these patients. Additionally, we will explore the change in other low molecular weight proteins [cystatin C, and NGAL in response to treatment with Ace Inh and ARB. We propose to test the hypothesis via the following specific aims:

Specific Aims:

- 1- We will determine the concentration of UFLCs (kappa and lambda) and UMACR in patients with DM with eGFR > 30 min/ml not on Ace Inh or ARB treatment.
- 2- We will determine the concentration of UFLCs (kappa and lambda) and UMACR in patients with DM with eGFR > 30 min/ml after treatment with Ace Inh and/or ARB for three months.
- 3- **Exploratory aim:** We will determine the concentration of urinary cystatin C and NGAL before and after treatment in the above patients to assess their response to Ace Inh and/or ARB class of drugs.

The **short term goal** of this study is to collect preliminary data on the effect that treatment with Ace Inh and ARB class of drugs have on UFLCs in comparison to UMACR. This data will be used to apply for funding for a longitudinal study to assess the effect of continuous treatment with Ace Inh and ARB on the levels of UFLCs in comparison to UMACR. The **long term goal** is to assess and compare UFLCs as a marker of kidney damage that can be used to diagnosis kidney disease earlier than UMACR; and if UFLCs can be used for prognosis and better prediction of progression to CKD.

Project Description - Introduction

Diabetes mellitus and kidney disease

Diabetes mellitus (DM) is one of the leading cause of chronic kidney disease (CKD)(7). It is estimated that by 2030, the annual number of patients receiving dialysis or who have had kidney transplants will exceed 2 million(11). From the 1988-1994 National Health and Nutrition Examination Survey (NHANES) data the prevalence of CKD in the US population aged > 20 years was 14.5%(12), which has increased to 16.8% according to the 1999-2004 NHANES data. Per practice recommendation, measuring albuminuria remain the key tools for screening diabetic patients for nephropathy. Albumin adjusted for urinary creatinine as assessed by the spot urine microalbumin creatinine ratio (UMACR) is used to diagnose (>30 ml/min) kidney disease, monitor progression of CKD and assess the adequacy of treatment of CKD Chronic kidney disease is defined as follows (ref): **Stage 1**: Normal GFR; GFR >90 mL/min/1.73 m² with other evidence of chronic kidney damage; **Stage 2**: Mild impairment; GFR 60-89 mL/min/1.73 m² with other evidence of chronic kidney damage; **Stage 3**: Moderate impairment; GFR 30-59 mL/min/1.73 m²; Stage 3 CKD should be split into two subcategories defined by (2): **Stage 4**: Severe impairment: GFR 15-29 mL/min/1.73 m²; **Stage 5**: Established renal failure (ERF): GFR <15 mL/min/1.73 m² or on dialysis (the term established renal failure is used instead of end-stage renal disease or end-stage renal failure).

Epidemiologic studies have demonstrated an association between poor glycemic control and kidney disease in patients with type 1 and type 2 DM (13;14). Studies have also shown that tight glycemic control slows the development of albuminuria, (15) and that improved glycemic control slows the rate of decrease in GFR.

Recently, in the intensive arm of the Action to Control Cardiovascular Risk in Diabetes (ACCORD) trial(4), there was no reduction in the incident CKD or ESRD despite the tight glycemic control. Data from Third NHANES demonstrated that albuminuria was absent in 36% of patients with DM and CKD (5).

Thus, evidence challenges the thinking that albuminuria as measured as UMACR will always precede progression to CKD. UMACR also does not predict which patients will progress and which not to CKD. UMACR can be elevated by tobacco use, obesity, recent exercise, urinary tract infection, heart failure, uncontrolled blood glucose and hematuria. There is interest in research on biomarker of tubulo-interstitial injury as the pathogenic mechanisms that lead to CKD converge on a common pathway, which is tubular atrophy (16).

Urine free light chains

Free light chains (FLCs) are bi-products of normal immunoglobulin synthesis(17;18) which are predominantly removed from the circulation by the kidneys. Light and heavy chains are used to make immunoglobulins. Light chains though are produced in excess of heavy chains. The unused light chains, also known as free light chains (kappa and lambda light chain) may be present to some degree in some individuals, but should not be found in the urine of individuals with normal renal function. This is true unless there is a condition resulting in the production of excess amount of free light chains (as in myeloma) is present or if the ability of the proximal tubules to reabsorb normally excreted free light chains is decreased.

FLCs are markers of inflammation and chronic inflammation is well recognized to be associated with diabetes(17). A normal range from healthy volunteers for the level of UFCs was established. A retrospective study conducted from patients recruited in the United Kingdom Asian Diabetes Study assessed polyclonal FLCs in patients with early diabetic kidney disease(7). Patients with T2DM had significantly raised concentrations of serum polyclonal FLCs before overt renal impairment developed ($p<0.001$). 68% of diabetic patients with normal urinary albumin: creatinine ratios (ACRs) had abnormal urinary FLC: creatinine ratios. The proportion of diabetic patients with abnormal FLC: creatinine ratios rose with increasing ACR. Both urinary FLC concentrations and FLC: creatinine ratios increased significantly with microalbuminuria and proteinuria. Data by [name](19) on cultured cells and rodents has shown that FLCs are more toxic to kidneys than albumin. However, there is no longitudinal data evaluating the effect of drugs that are known to be renoprotective on the FLCs. Since UFC are usually found in patients with an excess production of free light chains or in those with renal failure due to proximal tubular dysfunction, we hypothesized that free light chains would be produced in patients with diabetic nephropathy and the level of light chains in the urine may decrease with agents that are

renoprotective such as Ace Inh and ARB class of drugs. Ace Inh and ARBs are the first line therapy for treatment of kidney disease. There are limitations of UMACR that have led to an international working group to call for research into new biomarkers of diabetic nephropathy(6). To assess the utility of UFCs as a marker of diagnosis and prognosis of CKD, we propose the following specific aims:

Specific Aims:

- 1- We will determine the concentration of UFC (kappa and lambda) and UMACR in patients with DM with eGFR > 30 min/ml not on Ace Inh or ARB treatment.
- 2- We will determine the concentration of UFCs (kappa and lambda) and UMACR in patients with DM with eGFR > 30 min/ml after treatment with Ace Inh and/or ARB for three months.
- 3- **Exploratory aim:** We will do exploratory analysis on the levels of cystatin C and NGAL to assess the change in their levels after treatment with Ace Inh and/or ARBs and correlate it to the change in UMACR and UFCs in the above patients.

Innovation:

Whether albuminuria (as measured by the UMACR) is a good surrogate marker for progression of CKD in DM remains in question. There is a need for biomarkers that can detect kidney disease in earlier stages than UMACR and can reliably predict the progression of CKD. Analysis of biomarkers specific of tubulointerstitial kidney injury, the common pathway of progressive kidney disease will give us insight into the potential of such a surrogate marker of CKD. The presence of free light chains in the urine samples of patients with diabetes may be an indication of diabetic kidney disease if UMACR < 30. The effect of renoprotective drugs on UFCs warrants to be documented to follow these patients with CKD and thus explore the potential of UFC as a marker of kidney disease.

Supporting data

We hypothesized that urinary polyclonal free light chain excretion is elevated in early diabetic kidney as compared to controls and that urinary polyclonal free light chains excretion is elevated in early diabetic nephropathy before GFR declines. The objective was to investigate the excretion of urinary free light chains (UFC) in men and women, with and without DM, with a body mass index ≤ 27 or ≥ 30 . It was a cross-sectional study, with males and females between the ages of 18 and 70. Urine κ and λ FLC concentrations were measured by nephelometry, on a Dade-Behring BN™ II Analyzer using a particle-enhanced, high-specificity, homogenous immunoassay. In our study(20), there were three groups; controls (group I), obese without DM (group II), and obese with DM and HTN (group III). In group III, the mean HbA1c was $7.4 \pm 1.3\%$. See table 1 for the results.

Table 1: Results of the UFCs and UMACR

	I-Healthy Controls	II-Obese without DM	III- Obese with DM and HTN
N	10	40	30
Females	5	20	15
Age (years)	37.0 ± 10.5	45.7 ± 11.6	57.3 ± 7.0
BMI	22.5 ± 2.8	38.2 ± 7.5	41.6 ± 6.9
S. Creatinine (mg/dL)	0.79 ± 0.2	0.9 ± 0.3	0.9 ± 0.9
UMACR (mg/g)	9.2 ± 7.54	23.7 ± 61.6	27.2 ± 70.6
Urine Kappa (mg/L) ^{†*}	14.7 ± 11.1	34.0 ± 63.7	51.0 ± 71.8
Urine Kappa/Cr (mg/L) ^{†*}	0.01 ± 0.01	0.03 ± 0.06	0.04 ± 0.03
Urine Lambda (mg/L) [†]	5.8 ± 14.0	2.3 ± 3.9	8.7 ± 16.5
Urine Lambda/Cr (mg/L)	0.002 ± 0.003	0.002 ± 0.003	0.006 ± 0.013
Urine Kappa + Lambda (mg/L) [†]	20.4 ± 15.1	36.3 ± 66.9	59.7 ± 76.9
Urine Kappa + Lambda/Cr (mg/L) [†]	0.01 ± 0.01	0.02 ± 0.07	0.04 ± 0.04

UMACR= urine microalbumin creatinine ratio

† = $P < 0.05$ between groups I and III

* = Trend toward significance between groups I and II [(free Kappa, $P = 0.07$), Kappa/Cr, $P = 0.08$)]

Results suggest excretion of urinary polyclonal free light chains is increased in obese subjects with DM and hypertension as compared to normal controls.

Limitations of this data include the cross-sectional design and use of Ace Inh and/or ARB class of drugs by 75% of the subjects in groups II and III. Therefore, the effect of Ace Inh and/or ARBs on the mean change of UFCs as compared to UMACR could not be assessed.

Approach

The proposed research project is aimed at studying the effect of anti-hypertensive medications on UFCs as compared to UMACR. We will recruit subjects with CKD stages I, II, and III. This will allow us to have a direct comparison between the two variables (UFCs and UMACR) across the above three stages of CKD, excluding stages IV and V. The reason for excluding patients with stages IV and V is that decreased clearance of the UFCs will confound the results.

Inclusion Criteria:

- 1- Men and women with DM, type 1 or type 2.
- 2- Age 18- 75
- 3- Estimated glomerular filtration rate (eGFR) > 30 ml/min
- 4- Hypertension
- 5- Use of Ace Inh and ARB for control of blood pressure who are willing to be placed on alternate drug(s) in the washout period for blood pressure control.

[figure not shown]
Exclusion Criteria:

- 1- Pregnancy
- 2- Patients with chronic kidney disease stage with eGFR ≤ 30 ml/min (CKD stage IV and V)
- 3- Nephrotic range proteinuria (urinary protein > 3.5 gm/day)
- 4- History or renal transplantation
- 5- History of multiple myeloma
- 6- Known history of hypersensitivity reaction or intolerance to Ace Inh or ARB, Amlodipine, Terazosin, Hydrochlorothiazide, and/or Hydralazine.

Research Design

This is a prospective, interventional study involving patients with either type I or type 2 DM and hypertension, which will be recruited from the outpatient clinics and the Tulane volunteer registry. Patients who meet the inclusion criteria on evaluation of blood work in the last 90 days of the visit will then undergo screening.

Information from the most recent laboratory data will be collected. There will be no genetic testing. The study is designed to include patients with and without diabetic nephropathy. All pertinent medications will be recorded as this information will be very important in interpreting the results of the data analyses. Below is a schematic representation of the visit schedule.

Washout period

In the washout period, if Ace Inh or ARB classes of drug are part of patients' antihypertensive regimen, then the Ace Inh and/or ARB medication(s) will be discontinued. The patient will be started on alternative therapy (Amlodipine, Hydralazine, Terazosin and/or Hydrochlorothiazide) for control of their blood pressure. **The goal for their blood pressure will be set at < 140/90 mm/Hg.**

Test Period

On day 1 of the test period, patients will be advised not to take their blood pressure medication(s) prior to the study visit. During the study visit, urine sample will be collected for analysis of spot UFCs and spot UMACR. Additional 40 ml of urine and 10 ml of blood will be collected and stored for further analysis. The stored urine will be analyzed for cystatin C, NGAL. Urine and blood will be analyzed for other markers of obesity, diabetes, cardiovascular and kidney disease depending on the availability of funding.

After the blood and urine sample have been collected in a fasting state, those patients that were on Ace Inh or ARB prior to the washout period, will be started on the same regimen (Ace Inh and/or ARB). The alternate medication(s) that were started during the washout period will be discontinued.

Amlodipine, Hydrochlorothiazide, Hydralazine, Terazosin, Lisinopril and Losartan are all available in generic formulations. The dose of the drug and the decision to titrate the medication(s) for appropriate control and/or addition of medications will be decided by the principal investigator.

Methodology

Urine samples collected from patients will be aliquotted and stored in a -70oC deep freezer until the assays are performed. The following assays will be used to measure the respective markers.

- 1- A new latex-enhanced immunonephelometric assay measuring free k and l light chains as a free form (Freelite®, The Binding Site, San Diego, CA) has been developed. We have measure urinary polyclonal k and l FLC of immunoglobulins by the nephelometric immunoassay.
- 2- Microalbuminuria[Micro-albumin (MAB) (Orgentec Diagnostic, Mainz, Germany], and urinary excretion of low molecular weight proteins, cystatin C (CSC) (Arbor Assays, Ann Arbor, MI) and NGAL (R&D Systems, Minneapolis, MN) will be quantified by competitive solid phase enzyme immunoassay (ELISA) in accordance with the manufacturer's instructions.
- 3- Urinary creatinine (CRN) levels will be measured by Jaffe's method.
- 4- The urine free light chains: creatinine ratio as well as the urine microalbumin: creatinine ratio will be calculated and analyzed.

Analysis

Power and sample size

We plan to recruit 150 patients. Assumptions are: power = 0.8; alpha = 0.05, with 30% reduction in mean response being taken as significant. There is no data on the correlation of pre and post measures. We have set the correlation to 0.7 as Hutchison et al have demonstrated the correlation between urinary kappa and lambda light chains to be 0.88 with UMACR(7). The standard deviation from our data were \pm 72 mg/L for urinary kappa light chains and \pm 17 mg/L for urinary lambda chains in patients with DM and HTN. Assuming similar standard deviations in our sample for the proposed study, the sample size of 150 will allow us 80% power to detect a correlation coefficient of 0.7 between two normally distributed numerical variables when type I error is 5%.

Statistical analysis

Summary statistics such as mean, standard deviations, ranges, and percentiles of numerical variables will be given. Plots and goodness-of-fit tests will be generated to examine the distributions of the variables. Data will be log-transformed to normalized variables when necessary. If transformations do not resolve serious distribution problems, then nonparametric techniques will be considered as alternatives to parametric techniques. Outliers and influential points will be identified and examined.

Prevalence of incidence of interests will also be provided. Bar-plots and pie-charts will be produced for visual illustrations. Two-sample t-tests will be used to detect differences in numerical outcomes between groups, and chi-square tests will be employed to compare the frequencies of categorical outcomes. Linear or logistic regression models will be fitted to examine effects of covariates. Stepwise model selection methods will be used to identify for potential risk factors or prognostic variables. Residual analysis will be followed to validate the assumptions. All analyses will be performed using SAS version 9.1. Pearson or Spearman's correlation coefficients will be estimated between cystatin C and NGAL and traditional markers (blood pressure, lipids, UMACR, etc.) and UFCs.

This data will be presented in the form of poster(s) at scientific meeting(s) and used for peer reviewed publications and future grant applications.

Subject recruitment and safety

Patients will be recruited from the outpatient clinics and the Tulane volunteer registry. All patients will sign the informed consent prior to starting the study. **Data safety monitoring board** will be formed that will review the data every six months to ensure patient safety and recommend continuation or discontinuation in the study. All patient information and data will be stored in a safe place under lock and key.

The target of blood pressure for patients during the washout period of the study is < 140/90 mm/Hg as per treatment guidelines(10). It is important to change the medications, as Ace Inh and ARB are the first line therapy in patients with DM. Since the focus of the proposed project is to study the effect of Ace Inh and ARB on UFC, collection of UFC with Ace Inh and/or ARB will confound the results.

To address this, patients will be advised to check their blood pressure at least 3 times / week either at home or in a facility such as a pharmacy. Given the variability in the machines, they will be advised to be consistent about where they check their blood pressure. If the blood pressure is > 130/80 mm/Hg, they will be advised to contact the principal investigator. The principal investigator will then make appropriate changes to their medication regimen.

Significance

Inclusion of patients with many different clinical (DM and HTN, with and without nephropathy) and biochemical variables will allow us to evaluate the prevalence of these clinical and biochemical parameters, including albuminuria and relate it to the UFCs depending on the renal function. In those patients in whom UMACR < 30 upon entering the study, it will allow us to collect data on the effect of anti-hypertensive medications on UFCs before kidney damage starts as compared to UMACR. This cohort of patients can be followed over time to assess the utility of UFCs as a marker of kidney damage in comparison to UMACR. In those subjects, that do have established kidney damage (diagnosed by UMACR > 30); data collected at the end of the study will allow us to study the effect of anti-hypertensive medications on UFCs as compared to UMACR. The next step for this cohort of patients would be to follow them longitudinally to examine the role of UFCs as a prognostic marker of progression of kidney damage in comparison to UMACR. **Data from the proposed study will be used to apply for funding for a longitudinal study.**

Key Personnel

[name] (Co-Investigators) – have expertise in UFCs, kidney disease and have the necessary laboratory resources.

[name] (Consultant) – has expertise in DM, insulin resistance, obesity and conducting clinical trials.

Biostatistician (TBA) – we will consult with a biostatistician for data analyses and proper interpretation. The biostatistician will also help us use the obtained data for further grant application preparation.

Description of the relevance of the project to long-range goals

Public Health Relevance

There are now more than 385,000 people in the U.S. with ESRD and the burden of ESRD is growing. Treating ESRD imposes a large economic burden on patients, the health care system, and society. Diabetes mellitus is the leading cause of ESRD. There is evidence that earlier stages of CKD can be detected and treated and that adverse outcomes of CKD can be prevented or delayed(21) . Data on urinary free light chains, which are a marker of tubular dysfunction, is sparse with no data on the effect of treatment with Ace Inh and ARB on UFC. Obtaining such data as proposed in this translational research project is critical as Ace Inh and ARB class of drugs are the standard of care in the treatment of patients with DM and kidney disease. Data obtained from this study will be used to apply for peer-reviewed grant applications for funding for a larger, longitudinal study to study if UFC can be used as a prognostic marker in monitoring the progression and adequacy of treatment of kidney disease in comparison to urine microalbumin creatinine ratio. The long range goal is to study the utility of UFC as an early biomarker of kidney disease.

Relevance for Tulane investigators

[name] has been able to recruit 590 patients for her current study investigating obesity and biomarkers of kidney damage. Data from this cohort of patients has yielded preliminary results on several biomarkers and given insight into some disease processes linked to obesity associated kidney disease. [name] have expertise in urinary free light chains; and have laboratory equipment and resources available for running the assays for urinary free light chains. This study utilizes the expertise of investigators at Tulane with the common interest in finding biochemical monitoring modalities to detect kidney disease in the earlier stage and to find modalities to better monitor its progression.

In establishing this **collaboration** for pilot funding with [name] and obtaining preliminary data through the proposed **translational research project following the model of interdisciplinary research**, we will be able to apply for a longitudinal study investigating the role of UFC as a biomarker of kidney damage and prognosis.

Budget Request and Justification

Personnel	% Effort	Salary	Fringe	Total
Medical Research Technician	15%	\$ 3,675.00	\$ 827.00	\$ 4,502.00
Data Manager	2%	\$ 758.00	\$ 171.00	\$ 929.00
Research Coordinator	1%	\$ 585.00	\$ 132.00	\$ 717.00
Supplies/Materials				\$ 39,885.00
Travel				\$ 1,317.00
Publication Costs				\$ 150.00
IRB Fees				\$ 2,500.00
Total				\$ 50,000.00

Personnel

[name], MPH: Principal Investigator-is not requesting salary support.

Co-Investigators ([name], and [name], PhD), Consultant ([name]) and Biostatistician (TBA): are not requesting salary support.

[name]-Research Coordinator: 1% effort. Once patients are referred for the study, the coordinator will be responsible for following up with the patients, randomization, and scheduling study protocol related visits. The coordinator will be in close communication with the principal investigator of the study.

[name]-Data Manager: 2% effort. Will be responsible for obtaining and compiling the data in an accessible, but secure manner and location.

TBA-Medical Research Technician: 15% effort. Will be responsible for running urinary free light chain assays.

Supplies and Materials

Patient Visits: Patients will be given a \$25 reimbursement for travel expenses associated with each visit.

Patients are expected to have three visits in the course of the study which results in a total reimbursement of \$75 per patient. The study will include 150 patients; therefore, the total cost for patient reimbursements will be \$11,250.00.

Screening and Laboratory Tests: Each patient will receive three CMP tests at a cost of \$4.50 each for a total of \$2,025.00. Each patient will receive two lipid panels at the cost of \$10 each for a total of \$3,000.00.

Approximately 100 patients will receive a B-Hcg at a cost of \$13.35 each for a total of \$1,335.00. Each kit for UFC will test 30 patients, and each patient will receive one test; therefore, 5 kits will be needed at a cost of \$1,800.00 each for a total of \$9,000.00. Each kit for urine creatinine will test 30 patients, and each patient will receive one test; therefore, 5 kits will be needed at a cost of \$180.00 each for a total of \$900.00. Each kit for urine microalbumin will test 30 patients, and each patient will receive one test; therefore, 5 kits will be needed at a cost of \$475.00 each for a total of \$2,375.00. \$8,000 has been set aside for miscellaneous variables in exploratory analyses.

Medicine: Patients currently taking Ace Inh or ARBs as part of their daily regimen prior to the washout period will need to be taken off these drugs. The study is meant to study the effects of these drugs, so the patients' systems must be clear of them when the study begins. These patients will be placed on other drugs (hydralazine or terazosin) during the washout period.

Travel: Allotted funds will be used to travel to scientific meetings to present the data.

Anticipated timeline and completion

Months	1-6	7-12	13-18
Subject recruitment	X	X	X
Obtaining and analyzing pilot data		X	X
Presenting pilot data at scientific meetings		X	X
Peer-reviewed publications		X	X
Preparation of peer reviewed grant application(s) for a larger longitudinal study			X

Literature cited

1. http://www.cdc.gov/diabetes/pubs/pdf/nfds_2007.pdf. CDC website. 2011. 1-12-2011. Ref Type: Electronic Citation
2. KDOQI Clinical Practice Guidelines and Clinical Practice Recommendations for Diabetes and Chronic Kidney Disease. *Am J Kidney Dis* 2007;49:S12-154.
3. <http://www.cdc.gov/diabetes/pubs/factsheets/kidney.htm#7>. CDC website. 2011. 1-12-2011. Ref Type: Electronic Citation
5. Prevalence of chronic kidney disease and associated risk factors--United States, 1999-2004. *MMWR Morb Mortal Wkly Rep* 2007;56:161-5.
6. KDOQI working group. Clinical practice guidelines and clinical practice recommendations for diabetes and chronic kidney disease: research recommendations. *Am J Kidney Dis* 2007;49:140-3.

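### The before/after change in urinary free light chains is credited to Ace Inh/ARB, but the design can show only the effect of switching from the washout regimen, and no blood-pressure-adjusted analysis of that change is fixed

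*Combined protocol and SAP*

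**What the plan says.** The hypothesis on the specific aims page is causal: "treatment with Ace Inh and/or ARB will decrease UFLCs in these patients". The Subject recruitment and safety section likewise gives the effect of Ace Inh and ARB on free light chains as the focus. Aims 1 and 2 are descriptive: concentrations off these drugs, then "after treatment with Ace Inh and/or ARB for three months". The Approach section is looser: "The proposed research project is aimed at studying the effect of anti-hypertensive medications on UFCs as compared to UMACR".

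The baseline is not an untreated state. Under Washout period, Ace Inh/ARB is stopped and "The patient will be started on alternative therapy (Amlodipine, Hydralazine, Terazosin and/or Hydrochlorothiazide) for control of their blood pressure". Under Test Period, once the day-1 samples are taken, patients go back on the regimen they had before washout, and "The alternate medication(s) that were started during the washout period will be discontinued". The principal investigator then decides "The dose of the drug and the decision to titrate the medication(s) for appropriate control and/or addition of medications".

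Research Design says: "This is a prospective, interventional study involving patients with either type I or type 2 DM and hypertension". No control arm, sequence or allocation ratio is described. Randomization appears once, as a staff duty in the budget: "the coordinator will be responsible for following up with the patients, randomization, and scheduling study protocol related visits".

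The Statistical analysis section names two-sample t-tests between undefined groups, linear or logistic regression for unnamed covariates, and stepwise selection. Blood pressure is named there only as a correlate of cystatin C and NGAL. Research Design says that pertinent medications will be recorded and matter for interpretation, but no analysis is tied to them.

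**The concern.** Four things differ between the two samples: Ace Inh/ARB is on, the washout drugs are off, doses or added drugs may have changed, and three months have passed. The first two happen in one step in every patient who switches, so they are fully confounded within patient. Time is confounded with both.

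A difference in blood pressure between the periods, an effect of a withdrawn washout drug on light chain excretion, or drift would all be read as an effect of Ace Inh/ARB. The error can go either way: a non-drug shift upward would hide a true fall. The data are meant to support publications and an application for a longitudinal study, so a wrong attribution would be carried forward.

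**Working it through.** **Attribution.** The observed mean change is the sum of (a) starting Ace Inh/ARB, (b) stopping the washout drugs, (c) later titration and additions, and (d) time. With one group and two time points there is one mean change and four unknowns. A regression of the change on the change in blood pressure, Δ = a + b·ΔBP, gives a, the expected change when blood pressure does not move. That addresses one pathway. It leaves (b) and (d) inside a, because both apply to every patient who switches.

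**The plan's own sample size.** Inputs from Power and sample size: SD 72 mg/L for kappa and 17 for lambda, correlation 0.7, 30% reduction, power 0.8, alpha 0.05 (taken as two-sided). Means from Table 1, group III: 51.0 and 8.7 mg/L. For a paired test, n = [SD·√(2(1−r))·(1.960 + 0.842)/δ]².
- Kappa: [72 × 0.7746 × 2.802/15.3]² = 104.3, so 105.
- Lambda: [17 × 0.7746 × 2.802/2.61]² = 199.8, so 200.
- Detecting a correlation of 0.7 (Fisher z): (2.802/0.867)² + 3 = 13.4, so 14.

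The stated inputs do not give 150. Kappa with 30% dropout would (105/0.7 = 150), but the plan states no dropout. The point here does not depend on this; 150 is used below as the number of complete pairs.

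**How large a non-drug shift would pass as an effect (illustrative).** Assume a paired t-test on raw concentrations.
- Kappa: SE = 72 × √0.6/√150 = 55.77/12.25 = 4.55 mg/L. Critical observed shift = 1.976 × 4.55 = 9.0 mg/L, and 9.0/51 = 17.6%.
- Lambda: SE = 17 × √0.6/√150 = 1.075 mg/L. Critical observed shift = 2.12 mg/L, and 2.12/8.7 = 24.4%.

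With no Ace Inh/ARB effect at all, the chance of a significant result (noncentral t, noncentrality = shift × mean/SE) is:

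| Assumed true non-drug shift | 5% | 10% | 15% | 20% |
|---|---|---|---|---|
| Kappa, r = 0.7 | 9% | 20% | 39% | 60% |
| Kappa, r = 0.5 | 7% | 14% | 25% | 41% |
| Kappa, r = 0.88 | 14% | 42% | 75% | 94% |
| Lambda, r = 0.7 | 7% | 13% | 23% | 36% |

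The range of r is shown because the plan says that it has no data on the pre/post correlation.

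**If the named two-sample test were applied to the pre/post kappa data instead:** its SE is 72 × √(2/150) = 8.31, so the threshold is 1.968 × 8.31 = 16.4 mg/L (32%). The same four shifts would be declared significant 0.1, 0.7, 2.8 and 8.8% of the time.

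**The case against.** The best defence is that this is a pilot with descriptive aims, and a single-group before/after design is a visible choice. That stands, and no control arm is asked for. Splitting 150 into 75 per arm would give weak power for a 30% kappa difference by ANCOVA: SD 72 × √(1 − 0.49) = 51.4, SE 51.4 × √(2/75) = 8.40, 15.3/8.40 − 1.96 = −0.14, so about 44%. But the hypothesis and the stated focus are causal even though Aim 2 is not.

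A reader might infer more than the documents support:
- *That blood pressure cannot be analysed under the plan.* The generic covariate regression could hold it. The defect is that no outcome or covariate is named, and stepwise selection could drop it.
- *That Ace Inh/ARB dosing is unrestricted.* It restarts on the prior regimen; only later titration and additions are discretionary.
- *That blood pressure is uncontrolled or unrecorded.* The plan sets a washout goal below 140/90, asks for checks at least three times a week, and has patients call above 130/80. These limit a difference between periods without removing it. The goal and the call threshold differ and should be reconciled; no target is stated for the three months on Ace Inh/ARB. The visit schematic is not shown, so study-visit readings may be specified there.
- *That the trial has randomized arms.* One budget line is the only mention, and no arms are described.
- *That the rates above are the plan's false-positive rates.* The shifts are assumed. The plan names no paired test, allows log transformation, and also plans creatinine ratios. A true 17.6% shift would be significant only about half the time; the threshold applies to the observed shift.

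Adjusting for blood pressure is also open to challenge, because lower pressure is partly how these drugs may act. The adjusted estimate can therefore only be supportive.

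**Conclusion.** The point holds. Followed as written, the plan supports a statement about switching from the washout regimen to an Ace Inh/ARB-based regimen over three months. It does not support crediting the whole change to Ace Inh/ARB. This follows from the day-1 step and the absence of a described concurrent arm, and depends on no numerical assumption. No analysis of two time points can remove time drift.

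The size is illustrative only. It assumes a paired raw-scale test, the plan's SD and correlation, Table 1 means, 150 complete pairs and non-drug shifts that the documents do not give. On those terms a 10% kappa shift unrelated to Ace Inh/ARB would be called significant about 20% of the time, and a 20% shift about 60%. The change is worth making because it alters what the trial can conclude at almost no cost.

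**What to change.** 1. State the hypothesis and the conclusion as the change in UFLCs and UMACR on switching from the washout regimen to Ace Inh/ARB over three months. Name time and withdrawal of the washout drugs as alternatives that the design does not separate. Use the same wording in Approach and Significance, which now refer to antihypertensive drugs in general.
2. Keep the unadjusted paired change as the main result. Pre-specify one sensitivity regression of the UFLC change on the change in blood pressure, exempt from stepwise selection. Use readings at day 1 and month 3 (confirm against the visit schematic that they are collected) and the medications already recorded. Label it supportive, because blood pressure is partly a mediator.
3. Optional: store a urine aliquot at screening from patients still on their prior Ace Inh/ARB, for assay in a subset. An on-off-on pattern would argue against steady drift, though not against an effect of the washout drugs, which change at both switches. At the budget's kit prices a full extra round costs 5 × $1,800 + 5 × $180 = $9,900, more than the $8,000 set aside for exploratory work.

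Items 1 and 2 cost wording and one regression. The downside is a narrower claim.
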